The clinical and cost effectiveness of internet-delivered self-help Acceptance and Commitment Therapy for family carers of people with dementia (iACT4CARERS): A randomised controlled trial with ethnically diverse family carers

Phase 1 Study Protocol

Phase 1 protocol title: Views and experiences of ethnic minority family carers on

internet-delivered guided self-help Acceptance and Commitment Therapy for family carers of people with dementia (iACT4CARERS): A qualitative study

Protocol version and

date:

Version 1.1 / 12 July 2022

IRAS Number: 316137

Sponsor Number: R210595

Funders Number: NIHR150071

Sponsor: University of East Anglia

Research and Innovation Services

[name]

[name]

Funding information: This study is funded by the NIHR Health Technology

Assessment (HTA) (NIHR150071). The views expressed are those of the author(s) and not necessarily those of the NIHR

or the Department of Health and Social Care.

1. Context of the project

This study is part of a broader research project funded by the NIHR. In 2019, We received funding from the NIHR Research for Patient Benefit Programme (PB-PG-0418-20001) to (1) develop internet-delivered self-help Acceptance and Commitment Therapy (ACT) for family carers of people with dementia (iACT4CARERS), (2) explore whether iACT4CARERS is acceptable in this population, and (3) test whether it is feasible to deliver iACT4CARERS within NHS services. This feasibility study was successful, meeting all pre-defined criteria for progression from the feasibility study to a full-scale trial.

Following this, we received funding from the NIHR Health Technology Assessment (NIHR150071) to conduct a full-scale trial and evaluate the clinical- and cost-effectiveness of this new intervention, iACT4CARERS. This recently funded project (iACT4CARERS trial) consists of two phases (Phase 1 and 2) and has three key objectives.

- 1. To finalise iACT4CARERS based on recommendations from our feasibility study and Patient and Public Involvement (PPI) work (Phase 1).
- 2. To establish the clinical- and cost-effectiveness of iACT4CARERS plus TAU compared to TAU alone in an RCT with an internal pilot phase (Phase 2).
- 3. To assess fidelity and quality of implementation, establish causal mechanisms and identify contextual factors associated with variation in outcomes using the process evaluation approach (Phase 2).

This study protocol (ethics application) covers Phase 1 of the iACT4CARERS trial. The study protocol (ethics application) for Phase 2 of the project will be submitted separately in collaboration with the Norwich Critical Trials Unit at a later stage.

2. Background

2.1 What is the problem?

Previous systematic reviews led by the lead investigator ([name])[1, 2] demonstrated that the prevalence of anxiety and depression in family carers of people with dementia is around 32%. These estimates are substantially higher than reported prevalence rates in the general population in the UK[3] indicating a clear need for support with their mental health.

The current standard care pathway for mental health conditions in family carers of people with dementia includes self or GP referral to NHS psychological services[4]. However, many carers are not able to access timely psychological support due to various barriers such as mobility issues, lack of respite care and a shortage of skilled therapists leading to long waiting lists[5]. One way to address the clear need for improved access, and also scalability, is to design a service that can be delivered remotely, accessed independently at home, and at times chosen by the participant. Online treatments can do this.

Psychological treatments for carers of people with dementia, which have been previously tested such as the STrAtegies for RelaTives (START) intervention[6], are mainly delivered face-to-face and are based on conventional cognitive behaviour therapy (CBT). A recent review of in-person CBT for carers of people with dementia demonstrated a small to medium overall effect on depression (d=0.34)[7]. A meta-analysis focusing solely on technology-based self-help CBT for family carers of people with dementia demonstrated a small overall effect on depression (d=0.27)[8]. No significant overall effect was observed for anxiety in either review, suggesting that conventional CBT may have a limited effect on carer anxiety. These results suggest a need for improvement in psychological therapies among this population. We particularly need to identify the intervention that can (1) be delivered in a self-help format so that it is accessible by all for the reasons noted above and (2) effectively target anxiety to overcome challenges observed in previous studies.

2.2 Evidence explaining why this research is needed now

Acceptance and Commitment Therapy (ACT) is a form of psychotherapy with a strong evidence base for improving outcomes such as mood and quality of life in various populations, including people with anxiety, depression, chronic pain and somatic health problems[9-11]. ACT does not aim to change thoughts and feelings but rather to reduce avoidance and enhance personally meaningful behaviour. ACT achieves this by promoting psychological flexibility through three sets of skills, including the ability to (1) "step back" from restricting thoughts and allow painful emotions (i.e. OPEN); (2) focus on the present, connected with what is going on around us in the moment (i.e. AWARE); and (3) clarify and act on what is most important to do and build increasing patterns of effective values-based actions (i.e. ENGAGED)[12].

This strategic focus is highly practical because it is easier to change what we do, and how we do it, than to stop or change what we think[12]. As such, it has been argued that ACT is particularly useful for those living with immutable and chronic conditions[13]. Since many carers also face uncontrollable circumstances, ACT may be well suited to this population. Indeed, a recent systematic review on carer interventions, led by the lead investigator ([name])[14], demonstrated strong empirical support for face-to-face ACT in treating carer anxiety and depression.

Recent systematic reviews also suggest that ACT skills can be learnt online[15-17]. In the UK, co-investigator [name] was successful in converting manualised ACT for people with complex chronic pain to an online mode of delivery[18, 19]. This feasibility study led to

numerous enhancements of the treatment; the upgraded treatment was approved and implemented in the NHS just four years after the research began.

iACT4CARERS feasibility study

We received funding from the NIHR Research for Patient Benefit Programme (PB-PG-0418-20001) to (1) develop online self-help ACT for carers of people with dementia (iACT4CARERS; https://iact4carers.com), (2) explore whether iACT4CARERS is acceptable in this population, and (3) test whether it is feasible to deliver iACT4CARERS within NHS services. iACT4CARERS was offered on a self-learning basis, with minimal contact with a non-expert, minimally trained therapist.

Pre-defined criteria for progression from the feasibility study to a full-scale trial required iACT4CARERS to be deemed acceptable to carers as indicated by uptake and initial engagement (recruitment of 30 eligible carers over 6 months, with ≥70% completing at least two online sessions). These criteria were successfully met. Participant recruitment took place from August 2020 and January 2021 during the pandemic with 108 carers referred across three sites over six months. Thirty-three eligible carers were recruited, with ≥91% completing more than two sessions, suggesting excellent acceptability[20]. There was preliminary evidence of improvements in anxiety, depression and psychological flexibility, particularly in anxiety, which demonstrated an average reduction of 26% on the GAD7 anxiety scale (a reduction of 20% on GAD7 is considered to be a Minimum Clinically Important Difference[21]). Therefore, randomised controlled trial (RCT) evidence on clinical-and cost-effectiveness of this new intervention is warranted.

It is important to highlight that 76% (n=25/33) of eligible carers who received iACT4CARERS had self-referred from the community, and 24% of carers were referred from NHS services[20]. This suggests a substantial unmet need in the community, a desire to engage with interventions such as these, and perhaps a lack of carer identification (and/or carer support need identification) by formal healthcare services.

NHS and social care need

Currently, carers of people with dementia who receive the least support are those from ethnic minority groups. A recent systematic review of studies that included UK South Asian patients with dementia could not identify a single clinical trial of an intervention in this population, either for patients or carers[22]. Another recent systematic review suggested that female family members are often the main source of care in the South Asian communities, and since caregiving is seen as familial obligation within their culture, they are often reluctant to openly share their challenges and seek support[23]. An online approach such as iACT4CARERS has the potential to improve the psychological well-being of carers, cost effectiveness to NHS services, and importantly equity of access to care. Thus, a full-scale RCT to evaluate the effectiveness of iACT4CARERS in a diverse carer population is warranted.

This project is also timely and ethically justified from the perspective of the NHS and social care need. The NHS Long Term Plan (2019) sets the development of Integrated Care Systems to increasingly focus on population health as one of the top priorities[24]. This policy emphasises the need for preventative services, which individuals can access at a time and place that is convenient for them[25]. iACT4CARERS does not require highly trained expert therapists, and our feasibility study was successfully delivered within GP and NHS psychological services entirely remotely during the pandemic. This flexibility in delivery can address practical challenges currently faced by the NHS.

ACT with people from minority groups

A previous review, which explored cultural competence in ACT, suggested that ACT has been implemented across many countries including low-/middle-income countries such as

India and South Africa[26]. A recent study, which demonstrated the effectiveness of guided self-help ACT among South Sudanese refugees in a large RCT (n=694)[27], led to the development of non-guided self-help ACT for coping with adversity during the pandemic, and has been available on the website of the World Health Organisation in 11 different languages. A recent large trial (N=2,415), which involved 868 ethnic minority participants, also demonstrated that smartphone-delivered ACT was effective for smoking cessation[28]. These suggest that there is a strong potential for iACT4CARERS to be used with a diverse group of carers including those from ethnic minority groups.

PPI work we have undertaken

In collaboration with the Centre for Ethnic Health Research, we discussed iACT4CARERS with six PPI members who are carers of a family member with dementia from ethnic minority groups. All PPI members reported that they currently do not receive psychological support and expressed positive feelings about iACT4CARERS. However, some barriers were also identified.

The original version of iACT4CARERS had the option for carers to attend three peer support groups via video call. PPI members from ethnic minority groups expressed that (1) mental health issues are not openly discussed in some ethnic minority communities, particularly among male carers and (2) some female carers do not feel comfortable sharing personal issues with male carers. Therefore, it was suggested to include two brief (20-30 minutes) one-to-one sessions with the non-expert therapist via telephone or video call, where carers are encouraged to express their feelings and needs privately, rather than offering peer support groups.

3. Aims and objectives of the iACT4CARERS project

What is the clinical and cost effectiveness of iACT4CARERS in comparison to treatment-asusual (TAU) for reducing anxiety in carers of people with dementia?

Phase 1

 To finalise internet-delivered ACT for carers of people with dementia (iACT4CARERS) based on recommendations from our feasibility study and PPI work.

Phase 2

- To establish the clinical and cost effectiveness of iACT4CARERS plus TAU compared to TAU alone in a RCT with an internal pilot phase.
- To assess fidelity and quality of implementation, establish causal mechanisms and identify contextual factors associated with variation in outcomes using the process evaluation approach.

This study protocol (ethics application) covers Phase 1 of the iACT4CARERS trial. The study protocol (ethics application) for Phase 2 of the project will be submitted separately in collaboration with the Norwich Critical Trials Unit at a later stage.

4. Methods (Phase 1)

In Phase 1, we will follow a framework for the co-production of public health interventions[29] to finalise iACT4CARERS. Based on completed PPI work, optional online peer support groups will be removed. They will be replaced with two brief (20-30 minutes) one-to-one sessions with a therapist via telephone or video call. To gain preliminary feedback on acceptability and feasibility of this additional element (i.e. one-to-one sessions) of iAC4CARERS, the revised programme will be piloted with 10 carers from ethnic minority groups. Following this, iACT4CARERS will be finalised.

4.1 Research questions

- 1. What are the perceptions and experiences of additional one-to-one sessions embedded in iACT4CARERS among family carers of people with dementia from ethnic minority groups?
- 2. What are the perceptions and experiences of additional one-to-one sessions embedded in iACT4CARERS among therapists?

4.2 Sample

Purposeful sampling will be used. Ten family carers of people with dementia from ethnic minority groups will be selectively sampled for this study (sample size informed by the concept of Information Power[30]). Ethnic minorities refer to all ethnic groups except the white British group. A study on the incidence of dementia diagnosis in UK primary care demonstrated that 55% of those who received a diagnosis of dementia between 2007 and 2015 did not report their ethnicity[31]. Of those reported, 2% were from the Asian ethnic group. This patient group was the second largest group followed by the white British patient group. The steepest increase is expected particularly in South Asian communities in the coming years. Therefore, we aim to recruit at least five family carers from the Asian ethnic group.

Inclusion and exclusion criteria

The inclusion criteria are as follows:

- 1) Aged 18 and over: The content of iACT4CARERS is written for adults as the majority of family carers are in their 50s to 70s in the UK.
- 2) Identifying oneself as a carer from ethnic minority groups: Potential participants will be asked to confirm their ethnicity.
- 3) Caring for a family member diagnosed with dementia: Any family members including in-laws, such as daughters-in-law, will be eligible. The diagnosis of dementia will be based on the clinical information provided by the participant (carer). Potential participants will be asked to confirm whether the care recipient has received a formal diagnosis of dementia from a relevant healthcare professional. Potential participants will also be asked to confirm whether they provide regular care (self-defined) to the care recipient. No criteria will be set for frequency of care they provide, such as hours of caring per week, as the psychological impact of caring is related to multiple factors such as the relationship they have with the person with dementia. We will collect background and demographic data such as frequency of care they provide and their relationship to the care recipient.
- 4) Willing to complete iACT4CARERS: A brief description of the intervention will be included in the information sheet. Potential participants will be asked if they are willing to complete iACT4CARERS within 12 weeks and attend the interview session to provide feedback. Only those who are interested will be eligible.
- 5) Having access to the internet: Participants will need to have access to a computer, tablet, or smartphone connected to the internet. iACT4CARERS is accessible from any platform on any device, except for those devices that use an old operating system no longer supported as we cannot ensure the security of data. If participants do not have access to the internet through WiFi and need to use mobile data to access the internet, the relevant charge can be reimbursed (a maximum of £20 per participant).

The exclusion criteria are as follows:

- 1) Lacking capacity to provide fully informed written consent: Participants will be asked to provide consent in accordance with the Mental Capacity Act (2005). Participants will not be included in the study if they are unable to provide this.
- 2) Experiencing disabling medical or mental health problems making participation inappropriate or impractical: Potential participants will be asked to report any ongoing untreated condition during the screening session. The participant's GP will be informed of their involvement in the study, and any concerns raised by their GP regarding their involvement will be followed by a full discussion with the participant.
- 3) Expressing active suicidal intent: The risk of suicide will be assessed by a trained researcher during the initial assessment session. Those presenting suicidal ideation with active intent will be excluded.

Potential participants with insufficient understanding of English to complete screening measures and engage in the intervention will be encouraged to bring a family member who can support the participant and act as an interpreter. This approach was recommended by our Patient and Public Involvement (PPI) members from ethnic minority groups. If this option is not available, a professional interpreter can be arranged through the third company, which the University of East Anglia already has a contract in place.

4.3 Recruitment

Participants will be recruited through our collaborating partner, the Centre for Ethnic Health Research. The Centre for Ethnic Health Research is a research active organisation supported by the NIHR that aims to support research to reduce ethnic health inequalities. In order to reach a breadth of participants, the team from the Centre for Ethnic Health Research will use diverse channels of engagement to suit a variety of ethnic minority groups and accessibility needs. This will include the use of face-to-face, online and remote platforms for recruitment.

Potential recruitment strategies to be used by the Centre for Ethnic Health Research include:

- 1. The Centre for Ethnic Health Research Community Engagement Officers contacting their existing members (face to face -in accordance with Covid-19 rules; telephone, email, WhatsApp groups, etc.).
- 2. Advertising the study through the Centre for Ethnic Health Research's existing community networks and forums and partners, such as the voluntary sector and faith organisations.
- 3. Advertising the study through media (local, community radio stations, the Centre for Ethnic Health Research's social media channels).

Since this study only requires 10 participants, the first strategy (i.e. contact through Community Engagement Officers) will be prioritised. If the target is not met, wider recruitment such as community networks and media will be used. When potential participants express interest, the Centre for Ethnic Health Research will obtain consent for their contact detail to be shared with the researchers based at the University of East Anglia.

4.4 Participant timeline

Initial contact: Upon receipt of referrals, the researcher based at the University of East Anglia (UEA) will describe the study to potential participants and send an information pack consisting of an information sheet, eligibility checklist and consent form via email if they express an interest. The information pack can also be sent via post if preferred. The researcher will give a follow-up phone call to see if they have any questions.

Informed consent and initial assessment: Participants who opt to take part in the study will be asked to attend the initial assessment session via telephone or video call. During this session, potential participants will be asked to provide fully informed written consent either electronically or via post first. The consent form will include a series of statements asking that they have read the information sheet and meet the eligibility criteria (eligibility checklist). Once written consent has been obtained, potential participants will be asked to complete self-reported measures using an online or postal survey pack. These will include a demographic questionnaire, the Generalized Anxiety Disorder-7 (GAD7[32]) and the Patient Health Questionnaire-9 (PHQ9[33]). These variables will be used to characterise the sample. The risk of suicide will also be assessed by the trained researcher during the initial assessment session (further detailed in the ethical and regulatory considerations section).

iACT4CARERS intervention: Eligible participants will receive a link to the iACT4CARERS website and login details immediately after the initial assessment session via email (and post if requested). Unauthorised access to the intervention will be prevented by providing participants with unique login details. Participants will be instructed to complete eight online sessions within 12 weeks.

Participant interview: After the completion of iACT4CARERS, participants will be asked to attend an individual interview session via telephone or video call. Interviews will examine attitudes towards one-to-one sessions, suitability of their content, any impact they had on engagement with iACT4CARERS and any suggestions for improvement. First, participants will be asked to complete the Satisfaction With Therapy and Therapist Scale-Revised (STTS-R[34]), a 12-item self-report questionnaire assessing satisfaction with therapy and satisfaction with the therapist, either electronically or via post. Following this, the researcher will conduct the individual interview. The volume and quality of the audio recording will be checked at this point to ensure a clear recording. All interviews will be audio-recorded with the participant's permission. Handwritten field notes will also be used to record additional comments and observations during the session. The researcher will use a blended approach during the interview, which consists of passive interviewing (allowing the participant space and time to share their narrative) and more active approaches by using questions and prompts listed in the interview guide (attached to this ethics application). To end the interview, the researcher will allow a final opportunity for the participant to add or expand upon anything else that may have not yet been discussed. Closing remarks will be made, whereafter the interview will be concluded.

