4.5 Intervention

The iACT4CARERS intervention (https://iact4carers.com), which has been tested in our previous feasibility study funded by the NIHR will be used. Participants will be asked to complete eight online sessions within 12 weeks. Each session has three phases: self-learning, reflection and practice. The self-learning phase will guide carers through core ACT skills (OPEN, AWARE, and ENGAGED) that together constitute psychological flexibility. Interactive exercises to illustrate ACT skills will be presented using multiple modes (video/audio/text). The reflection phase encourages participants to reflect on exercises, which they found helpful and ask questions. Individually tailored written feedback will be provided by a therapist via the online programme to encourage continued practice each week. The practice phase allows participants to set a goal and practice ACT skills offline between online sessions.

Participants will be offered two brief (20-30 minutes) one-to-one sessions with a therapist via telephone or video call in addition to the online programme (iACT4CARERS). These one-to-one sessions will be provided at the beginning and middle of the intervention. Based on our previous feasibility study[35, 36] and completed PPI work, these brief one-to-one sessions will focus on encouraging family carers to: (1) express their feelings and emotional needs;

(2) share their challenges and concerns regarding the use of technology; and (3) discuss the expectation for weekly reflection and online feedback from their therapist so that support can be tailored.

Before the start of the therapist training, an intervention development group consisting of researchers (including PPI) and key stakeholders (including intended recipients/therapists) will co-produce the manual for these additional one-to-one sessions to ensure that all three topics listed above are covered during the sessions. This will involve presentation of the draft manual to all group members. Feedback will be sought, refinements made, and the manual presented again until final content is agreed.

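### Section 4.4 times the carer interview and satisfaction scale after programme completion and gives carers who stop early no stated route to feedback, so findings on acceptability and engagement risk being too favourable

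*Protocol*

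**What the plan says.** Protocol section 4.4, under the participant interview, sets the timing: "After the completion of iACT4CARERS, participants will be asked to attend an individual interview session via telephone or video call". The satisfaction measure belongs to the same session: "First, participants will be asked to complete the Satisfaction With Therapy and Therapist Scale-Revised". Among the interview topics is "any impact they had on engagement with iACT4CARERS and any suggestions for improvement", where the first part refers to the one-to-one sessions.

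Completion is described earlier in 4.4: "Participants will be instructed to complete eight online sessions within 12 weeks". Section 4.5 repeats the eight sessions and 12 weeks, and places the new element: "These one-to-one sessions will be provided at the beginning and middle of the intervention".

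Section 4.2 fixes the sample: "Ten family carers of people with dementia from ethnic minority groups will be selectively sampled for this study". Inclusion criterion 4 adds: "Potential participants will be asked if they are willing to complete iACT4CARERS within 12 weeks and attend the interview session to provide feedback". Only carers who are interested are eligible.

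Section 5 lets carers withdraw at any time, but describes no exit interview or exit questionnaire. Section 4.6 invites therapists to an interview at the end of the study, with no link to whether their carers finished. Section 4.8 plans a thematic analysis of the interviews and a descriptive summary of the questionnaires. It does not say how non-completers are handled.

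**The concern.** Section 4 gives the pilot's purpose as preliminary feedback on whether the added one-to-one sessions are acceptable and feasible. Research question 1 in section 4.1 asks for carers' own perceptions and experiences of them.

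Read literally, 4.4 obtains those views from carers who finished. Engagement is one of the things the interview explores, and it also helps decide who reaches the interview, so the interviewees would be selected partly on what is being studied. Criterion 4 already restricts entry to carers who say that they are willing to complete and be interviewed. A completion trigger would filter a second time in the same direction.

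Under section 4.8 the findings go to the intervention development group and the manual for the one-to-one sessions is then finalised. If the sessions put some carers off, those carers could have told the group what to change, and their views would be hard to recover later.

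**Working it through.** The protocol states no figure on this point to reproduce. The check has two parts: whether the text provides any other route to feedback, and how many of ten views might be lost.

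**1. Routes to carer feedback in the text**

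- Section 4.4, interview and STTS-R: after completion. No other trigger is given.
- Sections 4.4 and 4.5, completion: eight online sessions within 12 weeks.
- Section 5, withdrawal: permitted at any time. No feedback step is described.
- Section 4.5, timing of the one-to-one sessions: beginning and middle. A carer who stops after the first has experienced part of the new element, and one who stops after the midpoint may have experienced all of it.

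Some early stoppers would therefore have relevant experience and no stated way to report it.

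**2. Number of views at stake**

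Inputs: n = 10 carers (section 4.2) and a completion rate c. The protocol does not give c for all eight sessions, so a range of 0.70 to 0.90 is assumed.

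Expected non-completers = n × (1 − c). If carers stop independently, the chance of at least one non-completer = 1 − c^10.

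| Assumed c | Expected non-completers of 10 | Chance of at least one |
|---|---|---|
| 0.90 | 10 × 0.10 = 1 | 1 − 0.90^10 = 0.65 |
| 0.80 | 10 × 0.20 = 2 | 1 − 0.80^10 = 0.89 |
| 0.70 | 10 × 0.30 = 3 | 1 − 0.70^10 = 0.97 |

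The nearest figure in the protocol is from the feasibility study in section 2.2: "Thirty-three eligible carers were recruited, with ≥91% completing more than two sessions". This fits 30/33 = 90.9%. At 0.91, the expected number of ten who do not get past two sessions is 10 × 0.09 = 0.9, and the chance of at least one is 1 − 0.91^10 = 0.61. This is an illustration only. The figure is stated as a minimum, concerns more than two sessions rather than all eight, and comes from a programme that offered optional peer support groups instead of one-to-one sessions.

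These numbers show how many views may go uncollected. They do not measure bias in the findings.

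**The case against.** The strongest reply is that the gap is read from silence. Section 4.4 says that participants will be asked to attend and does not exclude anyone. Criterion 4 establishes every carer's willingness to be interviewed at entry. Completion could mean the end of the 12-week period. The Phase 1 flowchart, the interview guide and the information sheet were not available to this review, and any of them might settle the matter. This has force: the documents do not support saying that early stoppers are excluded by design, or that they will never be heard. What remains is that the text ties completion to the eight sessions and names no other trigger. If the wider reading is intended, it should be written down.

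Second, other evidence exists. Therapists deliver the sessions, are interviewed regardless of carer completion and could describe carers who disengaged. The development group includes PPI members and intended recipients. This softens the concern, but a therapist's account is indirect, and research question 1 asks for the carers' own views.

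Third, this is a ten-person qualitative pilot with purposeful sampling and no acceptability rate, threshold or progression rule. That also stands, and it limits how serious the point can be.

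A reader might also infer that a carer who declines the one-to-one calls is lost to the interview. The text does not support this. The calls are offered in addition to the online programme, so a carer who declines them but finishes the eight online sessions is still interviewed. Some carers for whom the new element did not work therefore can give a view.

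**Conclusion.** The point holds as a gap in a stated data-collection rule. Section 4.4 ties carer feedback to completion, and the protocol describes no route for carers who stop early. Findings on acceptability and engagement therefore risk being too favourable. At an assumed completion rate of 70% to 90%, 1 to 3 of ten views would be lost on average. That rests on the assumed range and on reading completion as the eight sessions.

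A reader might go further and conclude that acceptability will be overstated, for example that a true level of 70% to 90% would be reported as 100%. The documents do not support this. Phase 1 plans no such percentage. The scenario also needs every completer to approve of the sessions and every non-completer to reject them, while carers may stop for unrelated reasons. The direction of bias is plausible; its size cannot be stated.

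This is a worthwhile, inexpensive improvement to a small qualitative study, not a defect that undermines it.

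**What to change.** State in section 4.4 that every carer given login details is invited, if willing, to the STTS-R and interview at the earliest of completing the programme, stopping, or reaching 12 weeks. Report the number who stopped early, with reasons where offered. If completion was meant as the end of the 12-week period, the same sentence makes that clear.

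The cost is about one sentence in the protocol and perhaps small edits to the information sheet and interview guide. The number of carers stays at ten, so the number of carer interviews cannot exceed ten. Some early stoppers will decline, so the selection is reduced rather than removed, and reporting how many stopped lets readers judge what remains. Splitting results by completers and non-completers, or counting carers who declined at first approach, is optional and not needed to close this gap.
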